All patients were prepared with a 2-L polyethylene glycol plus ascorbic acid solution (Coolprep®, Taejoon Pharm., Seoul, Korea). All colonoscopy was performed by two highly experienced endoscopists ([name] and [name]) using a high-definition endoscope (CF-HQ290I, CF-H260AI, or PCF-Q260AZI; Olympus Co, Japan). The morphology of the polyp was described by Paris classification. The size of a detected polyp was measured using the opening width of the biopsy forceps. When an eligible polyp (a 5-10 mm polyp with NICE classification II) were detected, it was randomly allocated to either HSP or EMR group. An oval snare (SnareMaster®, Olympus Co, Japan or Optimos®, Taewoong Co, Korea) with Endocut or Forced Coagulation current of an electrosurgical unit (VIO300D; Erbe Elektromedizin GmbH, Tubingen, Germany) was used for polypectomy. When the polyp was assigned to EMR group, submucosal injection with normal saline was performed in advance of polypectomy. The resected specimen was retrieved using endoscope suction channel. Two biopsies were obtained

from the most probable residual tissue at the polypectomy site after irrigation, air inflation, and close observation with white-light and narrow-band imaging. Each patient was allowed for enrollment of a maximum of 2 sequential polyps from the cecum.

Immediate bleeding indicates continuous bleeding over 30 seconds requiring any form of endoscopic hemostasis (epinephrine injection, clipping or coagulation) immediately or within 24 hours after polypectomy whereas delayed bleeding was defined as bleeding from the post-polypectomy site between 24 hours and 2 weeks after polypectomy.

The resected specimens and biopsy specimens were reviewed by 3 highly-experienced gastrointestinal pathologists who were blinded to the clinical information and resection techniques for evaluation the involvement of adenomatous tissue at the resection margin. Complete resection was defined as absence of neoplastic tissue from the two additional biopsies of the polypectomy site whereas involvement of resection margin was defined as absence of neoplastic tissue at the margin of the resected specimen. When the involvement of resection margin could not be determined because of electrocautery effect or tangential tissue section, it was classified as “inconclusive.”

Study outcomes

The primary study outcome was a comparison of complete resection rates between two polypectomy techniques.

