The secondary outcomes included involvement of resection margin and post-polypectomy adverse events including immediate/delayed bleeding and perforation between the two groups.

Sample size calculation and statistical analysis

There was no exact report of the incomplete resection rate of HSP and EMR for 5-10 mm neoplastic polyps at the time of the study design. We assumed the incomplete resection rate of HSP to be 15% and that of EMR was 5%. Estimated sample size was 310 polyps (155 per group) with a α -value of 0.05, power of 80%, and a 10% of dropout rate.

Chi-square test or the Fisher’s exact test was used to compare categorical variables. The unpaired 2-sample t test was used for continuous variables. Binary logistic regression was used for multivariate analysis. All data analyses were performed by using Statistical Package for the Social Science for Windows (version 24, IBM corp. SPSS Inc, Chicago, Ill, US).

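### The only definition of margin involvement, a named secondary outcome, says *absence* of neoplastic tissue where it must say *presence*

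*Combined protocol and SAP*

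**What the plan says.** The Procedures section defines two pathology outcomes in a single sentence. The first half reads "Complete resection was defined as absence of neoplastic tissue from the two additional biopsies of the polypectomy site whereas", and the second half continues that "involvement of resection margin was defined as absence of neoplastic tissue at the margin of the resected specimen".

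The sentence before it gives the blinded pathologists' task as "evaluation the involvement of adenomatous tissue at the resection margin". The sentence after it creates a third class, inconclusive, which applies "When the involvement of resection margin could not be determined because of electrocautery effect or tangential tissue section".

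Under Study outcomes, the primary outcome is the complete resection rate. Margin involvement is secondary: "The secondary outcomes included involvement of resection margin and post-polypectomy adverse events including immediate/delayed bleeding and perforation between the two groups". No other definition of it is given. Categorical outcomes are compared by chi-square or Fisher's test.

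**The concern.** A margin is involved when neoplastic tissue is found there. The written definition says the opposite. *Absence* is right in the first half of the sentence, which defines the favourable outcome. It has been carried into the second half, which defines the unfavourable one, although the conjunction between them announces a contrast.

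An outcome definition is the rule from which an analyst codes the data and an outside reader interprets the table. Here the literal rule and the evident intent give opposite codes for every margin that can be determined. If the literal rule were used, the technique with more positive margins would appear to have fewer. The planned tests would give no warning, because a two-by-two test does not depend on which column is called the event.

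**Working it through.** **1. The texts side by side (all in Procedures).**

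| Place | What it implies for involvement |
|---|---|
| Pathologists' task | Adenomatous tissue present at the margin |
| Complete resection, first half of the sentence | *Absence* marks the good result, and a contrast follows |
| Margin involvement, second half of the sentence | *Absence* again, now attached to the bad result |
| Inconclusive class | Involvement could not be determined; silent on direction |

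The first two rows point to *presence*, the third states the reverse and the fourth does not settle it. Nothing under Study outcomes or in the statistical section corrects the third row.

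**2. The plan's own figure.** The sample size uses incomplete resection of 15% versus 5%, alpha 0.05, power 80% and 10% dropout. A two-sided comparison of two proportions with pooled variance and no continuity correction needs 141 per group. Inflation for dropout gives 141/0.9, rounded up to 157, or 141 × 1.1, rounded up to 156. The stated 155 per group is reproduced closely. It rests only on the biopsy-based primary outcome, so correcting the margin definition does not change it.

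**3. Effect among determinable margins.** Let Y = 1 if the margin is truly involved. The written rule records 1 − Y. Each arm's rate p becomes 1 − p, the difference d becomes −d, the odds ratio becomes 1/OR, and the chi-square and Fisher p-values are unchanged.

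The documents give no margin rates, so the counts below are assumptions, with 155 determinable margins per group. Hot snare polypectomy (HSP) is listed first and EMR second; p is from the uncorrected chi-square test.

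| True involved | Scored as written | OR, true to written | p, both ways |
|---|---|---|---|
| 8 vs 3 (5.2% vs 1.9%) | 147 vs 152 (94.8% vs 98.1%) | 2.76 to 0.36 | 0.125 |
| 23 vs 8 (14.8% vs 5.2%) | 132 vs 147 (85.2% vs 94.8%) | 3.20 to 0.31 | 0.0045 |
| 46 vs 31 (29.7% vs 20.0%) | 109 vs 124 (70.3% vs 80.0%) | 1.69 to 0.59 | 0.049 |

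For the middle row, OR = (23 × 147)/(8 × 132) = 3.20, and with the columns swapped (132 × 8)/(147 × 23) = 0.31. The difference goes from +9.7 to −9.7 points. Fisher's p is 0.0072 both ways.

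**4. Effect if inconclusive margins stay in the denominator.** The plan does not say whether they do. With q the inconclusive fraction and i the truly involved fraction of all polyps, the written rule gives a rate of 1 − q − i. The written difference (HSP minus EMR) is therefore (q_EMR − q_HSP) − d. For d > 0 the direction reverses only when q_EMR − q_HSP is smaller than d.

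The next table assumes about 15% versus 5% involved among determinable margins, with 155 polyps per group as the denominator.

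| Inconclusive, HSP / EMR | Written rates | Written difference (points) | True difference (points) |
|---|---|---|---|
| 16 / 16 | 76.1% vs 85.2% | −9.0 | +9.0 |
| 8 / 16 | 80.6% vs 85.2% | −4.5 | +9.7 |
| 16 / 31 | 76.1% vs 76.1% | 0.0 | +9.7 |
| 16 / 46 | 76.1% vs 67.1% | +9.0 | +10.3 |

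On this denominator, a reader who suspects the reversal cannot undo it by changing the sign. The inconclusive counts by arm are also needed.

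**The case against.** The best reply is that this is a slip any reader will correct. The term itself, the contrast within the sentence and the sentence before it all show the intent. A gastrointestinal pathologist is unlikely to report a clear margin as involved. The document is dated August 2019 and describes, in the past tense, a trial that ran to December 2017, so the coding was probably done from the pathology reports. A reversal would also show itself as implausibly high involvement rates. All of this is fair, and it makes actual reverse coding unlikely. It does not make the definition right, and the documents cannot show which rule was applied.

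Two objections to the numbers also stand. The rates are invented for illustration, and the middle scenario only mirrors the 15% and 5% assumed for a different outcome. In addition, 155 is the planned number of polyps per group including the dropout allowance, so fewer margins would be determinable. With 140 per group, 42 versus 28 involved (30% versus 20%) gives chi-square 3.73 and p of about 0.053, on the other side of 0.05 from the 0.049 above. The individual p-values should carry no weight. The reversal is an identity and holds for any rates and any group size.

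Finally, reporting inconclusive margins by arm goes beyond the wording error. That is correct: it is a useful addition, and the point does not depend on it.

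**Conclusion.** The concern holds. The definition is wrong as written and should be corrected. Among determinable margins, literal use turns each rate p into 1 − p, reverses the sign of the difference and inverts the odds ratio at an unchanged p-value; no assumption about rates is needed for that. The sizes shown, such as 14.8% versus 5.2% becoming 85.2% versus 94.8%, rest on assumed counts. If inconclusive margins are kept in the denominator, the distortion also depends on how they split between arms, and the direction need not reverse.

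The reach is limited to one secondary outcome. The primary outcome, its test and the sample size are untouched, and there is no evidence that the data were coded in reverse.

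**What to change.** - In Procedures, change *absence* to *presence* in the margin-involvement definition, and keep involvement as the named outcome.
- Check once, against the pathology reports, that the dataset and the reported tables code involved margins as neoplastic tissue present, and record the result.
- Preferably, report clear, involved and inconclusive margins as three counts per arm, so that the rate can be read on either denominator.

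The cost is one word, one coding check and one table row. No new data are needed, and neither the primary outcome nor the sample size changes.

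### The only stated comparison for bleeding and perforation is a chi-square or Fisher p-value; if these events are rare, a non-significant result will say little about relative safety

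*Combined protocol and SAP*

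**What the plan says.** Under Study outcomes, the combined protocol and SAP lists resection-margin involvement and "post-polypectomy adverse events including immediate/delayed bleeding and perforation between the two groups" as secondary outcomes. Under Sample size calculation and statistical analysis, the stated method for categorical outcomes is a chi-square or Fisher "exact test was used to compare categorical variables". No rule is given for choosing between the two. The section adds that "Binary logistic regression was used for multivariate analysis", without saying for which outcome.

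The sample size rests only on the primary outcome: incomplete resection of 15% with HSP and 5% with EMR, an "α -value of 0.05", 80% power and "a 10% of dropout rate". That leads to 310 polyps, 155 per arm. For bleeding and perforation the plan gives no expected rate, target difference, margin, power, risk difference or interval.

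The Procedures section defines immediate bleeding as bleeding that lasts more than 30 seconds and needs endoscopic hemostasis, up to 24 hours. Delayed bleeding runs from 24 hours to 2 weeks. Each patient may contribute up to 2 polyps.

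**The concern.** EMR adds a submucosal injection, so readers will want to know what it does to complications as well as to completeness. The planned output on that question is a p-value from a trial that was not sized for it. With few events, a p-value above 0.05 can mean that the arms are similar, or that the trial could not have told them apart. The p-value does not separate the two. An interval does, because it shows the largest difference the data leave open. Without one, a non-significant result can easily be read as similar safety.

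**Working it through.** **Inputs from the plan:** 155 polyps per arm; alpha 0.05, taken as two-sided because the sidedness is not stated; chi-square or Fisher test; 10% dropout, so about 155 × 0.9 = 139.5 evaluable per arm.

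**Assumptions made here:** adverse-event rates, since the documents give none, and independence between polyps.

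**1. The plan's own sample size.** The two-sided pooled formula for 15% v 5% is

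n = [1.960·√(2 × 0.10 × 0.90) + 0.842·√(0.15 × 0.85 + 0.05 × 0.95)]² / 0.10² = 140.1 per arm.

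Then 140.1 × 1.10 = 154.1, which rounds up to the stated 155. The figure is reproduced, and it confirms that the sidedness is two and that safety played no part in the size.

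**2. Smallest significant result when one arm has no events.** For s v 0 events with 155 per arm, the two-sided Fisher p is 2 × C(155, s) / C(310, s). The uncorrected chi-square statistic is 310·s / (310 − s).

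| Events | Fisher p | Chi-square | Chi-square p |
|---|---|---|---|
| 4 v 0 | not below 0.05 | 1240/306 = 4.05 | 0.044 |
| 5 v 0 | 0.060 | 1550/305 = 5.08 | 0.024 |
| 6 v 0 | 0.030 | – | – |

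Fisher therefore needs at least 6 v 0, which is 6/155 = 3.9% v 0%. At 140 evaluable per arm the values are 0.0603 and 0.0296, so the threshold is unchanged. With events in both arms, Fisher needs 8 v 1 (p = 0.036), 10 v 2 (0.035) or 12 v 3 (0.031). Yates-corrected chi-square also crosses at 6 v 0 (p = 0.039); the uncorrected test crosses at 4 v 0.

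**3. Power.** Binomial probabilities were summed over all 2×2 tables with p < 0.05.

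| Assumed rates | Fisher, 155 per arm | Fisher, 140 per arm | Uncorrected chi-square, 155 per arm |
|---|---|---|---|
| 0.5% v 1% | 0.2% | 0.2% | 3.5% |
| 1% v 3% | 10% | 8% | 22% |
| 0% v 3% | 32% | 24% | – |
| 2% v 6% | 32% | 28% | 44% |
| 1% v 5% | 41% | 36% | 55% |
| 3% v 10% | 65% | 59% | 72% |
| 5% v 15% | 81% | 76% | 86% |

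**4. What an interval would show.**

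- One arm with 0/155: the exact two-sided 95% upper limit is 1 − 0.025^(1/155) = 2.4%.
- 0 v 0 events: each Wilson upper limit is z²/(n + z²) = 3.84/158.84 = 2.4%, so the Newcombe interval for the difference is ±2.4 points (±2.7 at 140 per arm).
- 1 v 3 events: the difference is 1.94% − 0.65% = 1.29 points. The Wilson limits are 0.11% to 3.56% and 0.66% to 5.54%.
  - Lower limit: 1.29 − √[(1.94 − 0.66)² + (3.56 − 0.65)²] = −1.9 points.
  - Upper limit: 1.29 + √[(5.54 − 1.94)² + (0.65 − 0.11)²] = +4.9 points.
- For the same 1 v 3 table, Fisher gives p = 1 − C(155,2)²/C(310,4) = 1 − 0.377 = 0.62. That p-value gives no hint that a difference of nearly 5 points remains possible.

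**The case against.** **The event rates are assumed.** A reader might infer that the safety comparison will come out non-significant whatever the truth. The documents do not support that. They give no adverse-event rate, and immediate bleeding that needs any endoscopic hemostasis within 24 hours need not be as rare as perforation. At 3% v 10% or 5% v 15% Fisher has 65% or 81% power. Even among low rates, 0% v 3% gives 32%. This objection stands, and it confines the point to rare events.

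**The 6 v 0 threshold belongs to Fisher.** The plan allows either test, and uncorrected chi-square reaches p = 0.044 at 4 v 0. This also stands, although with 2 expected events per arm Fisher would be the usual choice. The missing selection rule is a small weakness of its own: at 5 v 0 the choice decides significance (0.024 or 0.060).

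**The plan draws no conclusion of equal safety.** That is correct. It names no equivalence or non-inferiority aim for these outcomes. The risk lies in how a bare p-value would be read, not in a claim the plan makes.

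**Readers can compute intervals from the counts.** They can if counts and denominators are published. What is missing is a planned estimate, not necessarily the data.

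**Logistic regression is also planned.** It is tied to no outcome and would help little with sparse counts.

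**Fisher's test is valid.** It is conservative here: its actual error rate at 155 per arm is about 0.2% with events at 1% in both arms, and 1.2% at 2%. Conservative is not wrong, and the number of events limits the information more than the choice of test does.

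**Conclusion.** The point holds for rare events. The plan states only a test for the secondary safety outcomes, without an estimate or interval. If rates are about 3% or less per arm, Fisher's test needs at least 6 v 0 and has about 10% power at 1% v 3%, so non-significance would be weak evidence of similar safety. It does not hold as a general statement about all three outcomes, because power rises to 41% at 1% v 5% and 81% at 5% v 15%.

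The conclusion rests on assumed event rates, a two-sided 5% level and independent polyps. None of the figures adjusts for two polyps from one patient. The primary outcome, the sample size and the validity of the named tests are unaffected.

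**What to change.** For immediate bleeding, delayed bleeding and perforation separately:

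1. Report events and denominators per arm, with the rate and an exact (Clopper-Pearson) 95% interval.
2. Make the risk difference with a Newcombe or score 95% interval the main safety result. State that polyps are treated as independent although a patient may contribute two.
3. Word the conclusion by the largest difference not excluded, and do not describe a non-significant p-value as similar safety.
4. Keep the planned p-value as secondary, and state the rule for choosing chi-square or Fisher.

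The methods can disagree near the boundary. At 5 v 0 the Newcombe interval is +0.2 to +7.3 points while Fisher gives p = 0.060. The interval should be read for its limits, not used as a replacement significance test.

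Boschloo's exact test is not needed for this fix. It would raise power only from 10% to 15% at 1% v 3%. The Methods section puts the end of the study at December 2017 and the document is dated August 2019, so replacing a named test with one that moves 5 v 0 from p = 0.060 to 0.047 would invite a charge of post hoc selection. It could be offered as a supplementary analysis, labelled as such.

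The cost is a few sentences in the plan and a few lines of code, with no new data. The downside is that, with few events, the intervals will show that differences of about 2 to 5 points cannot be excluded.
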